7.2 CONCOMITANT DISEASES AND MEDICATION

Only descriptive statistics are planned for this section of the CTR, based on the RS. Additionally, concomitant medication will also be displayed for DKD and non-DKD populations of the RS, respectively.

Concomitant diseases and concomitant non-drug therapies will be coded according to the most recent version of the Medical Dictionary for Regulatory Activities (MedDRA). Concomitant medication will be coded according to the most recent version of the World Health Organisation – Drug Dictionary. The coding version number will be displayed as a footnote in the respective output.

The frequency [N (%)] of patients with different concomitant diseases (baseline conditions) will be presented.

A medication/non-drug therapy will be considered concomitant to treatment if it:

- Is ongoing at the start of randomised trial treatment of BI 690517 or
- Starts within the on-treatment period (see [Section 6.1](#) for a definition of study analysis phases).

A medication/non-drug therapy will be considered as prior medication/non-drug therapy, if the end date of the medication/therapy is at any time prior to the start of the randomised trial treatment of BI 690517.

Concomitant medication use will be summarised with frequency and percentage of patients by ATC3 class and preferred name. Summaries will be presented for concomitant medication starting any time prior to start of trial treatment and starting any time during the BI 690517 on-treatment period (see [Section 6.1](#) for definition of the on-treatment period).

Concomitant use of non-drug therapies will be summarised with frequency and percentage. Summaries will be presented for concomitant non-drug therapies starting any time prior to start of trial treatment of BI 690517 and starting any time during the BI690517 on-treatment period (see [Section 6.1](#) for definition of the on-treatment period).

Restrictions regarding concomitant treatment during the study periods are defined in Section 4.2.2.1 of the CTP.

7.3 TREATMENT COMPLIANCE

Only descriptive statistics are planned according to percentage of patients meeting the compliance.

Compliance of BI 690517 will be displayed by weighted average of percent compliance, where the weight is defined as the time interval (number of weeks) between two consecutive study visits at which compliance data will be collected, i.e., the weight will be 1 (week) for visit 6 and visit 7, and will be 4 (weeks) for visit 8, visit 9, and visit EoT, respectively. Number and percentage of patients with compliance categories <80%, 80%-120%, and >120% will also be presented.

Compliance of empagliflozin will be displayed by percent of calculated compliance based on study medication taken according to protocol for each visit.

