²⁰To confirm eligibility, at visit 1, UACR measured in spot urine (midstream urine sample) by the central laboratory will be used. Should the first test for UACR at screening not match inclusion criteria due to UACR variability, this can be repeated once. If the second result does not meet the eligibility criteria the patient should be screen failed.

²¹Please refer to [FMV and 24-hour Urine Sampling Flowchart](#).

²²Patients will need to complete a paper diary at home in the 2 days prior to [Flow Chart](#) to record times of trial drug intake. Patients will also need to record start and stop times for 24-hour urine samples in a paper diary before Visit 5 and EOT.

²³ Study medication at Visit 4, Visit 6 and EoT will be taken from the medication kit supplied at the previous visit as there is no dispensing at these visits. At all other visits, study medication should be taken from the kit dispensed at the visit.

²⁴ All AEs, SAEs and AESI will be collected from informed consent until FUp1 (end of residual effect period). Please see [section 5.2.6.2.1](#).

²⁵ After FUp1 until the individual patient's end of trial, the investigator should report any cancers of new histology and exacerbations of existing cancer, all trial treatment related SAEs and trial treatment related AESIs. Please see [section 5.2.6.2.1](#).

²⁶ After the individual patient's end of trial, the investigator does not need to actively monitor the patient for new AEs but should report any occurrence of cancer and trial treatment related SAEs and trial treatment related AESIs of which the investigator may become aware of by any means of communication, e.g. phone call. Those AEs should be reported on the BI SAE form, but not on the CRF.

²⁷ In the case of premature discontinuation during the Randomised Run-in Period, FUp1.1, FUp1.2 and FUp2 do not need to be conducted.

²⁸ At Visits 4 and 5, only compliance to Empagliflozin/placebo will be calculated. At Visits 6, 7, 8, 9 and EOT, compliance will be calculated for both Empagliflozin/placebo and BI 690517/placebo.

²⁹ Days and associated time windows are relative to Visit 5.

FMV AND 24-HOUR URINE SAMPLING FLOW CHART

All samples listed in the following table should be collected by the patient, unless the patient is not able to do it.

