4.3 TREATMENT COMPLIANCE

Patients are requested to bring all remaining trial medication including empty package material with them when attending visits.

Based on tablet counts, treatment compliance will be calculated separately for both empagliflozin and BI 690517 (or matching placebo) as shown in the formula below.

$$\text{Treatment compliance (\%)} = \frac{\text{Number of tablets actually taken} \times 100}{\text{Number of tablets which should have been taken as directed by the investigator}}$$

If the number of doses taken is not between 80-120%, site staff will explain to the patient the importance of treatment compliance.

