6.2.5 Early discontinuation of Treatment

Patients who discontinue empagliflozin/placebo prematurely during the Run-In Period and who do not withdraw their informed consent; and patients who discontinue both empagliflozin/placebo and BI 690517/placebo during the Treatment Period and who do not withdraw their informed consent, should return for an End of Treatment (EoT) visit.

If the patient prematurely discontinues empagliflozin/placebo during the Run-In Period:

- If the patient has stopped taking empagliflozin/placebo the day of a scheduled visit or one day prior, the scheduled visit should be performed as an EoT Visit. Empagliflozin PK and safety samples should be collected. Biomarker, BI 690517 PK, aldosterone and optional biobanking samples do not need to be collected.
- If early discontinuation does not coincide with a scheduled visit, the patient should return for an EoT visit. PK, aldosterone, biomarker and optional biobanking samples do not need to be collected, but all safety assessments must be performed as indicated in the [Flow Chart](#).
- The 24-hour urine sample prior to EoT does not need to be collected.

If the patient prematurely discontinues empagliflozin/placebo and BI 690517/placebo during the Treatment Period:

- If the patient has stopped taking trial drugs the day of a scheduled visit or one day prior, the scheduled visit should be performed as an EoT Visit. All samples including PK, aldosterone profile and all biomarkers should be collected in addition to safety samples.
- If the early discontinuation does not coincide with a scheduled visit, the patient should return for an EoT Visit. PK, aldosterone, biomarker and optional biobanking samples do not need to be collected, but all safety assessments must be performed as indicated in the [Flow Chart](#).

After the EoT visit, all patients will start the off-treatment Follow-up Period (see [section 5.2.6](#)).

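### The listed BI 690517 compliance weights (1, 1, 4, 4, 4 weeks) can give a few directed doses the weight of four weeks and so misclassify some patients who stop early or interrupt

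*SAP*

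**What the plan says.** SAP 7.3 gives a definition and then a list. By the definition, "the weight is defined as the time interval (number of weeks) between two consecutive study visits at which compliance data will be collected". By the list, "the weight will be 1 (week) for visit 6 and visit 7" and it "will be 4 (weeks) for visit 8, visit 9, and visit EoT". The resulting figure is also categorised: "Number and percentage of patients with compliance categories <80%, 80%-120%, and >120% will also be presented".

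The per-visit percentage comes from Protocol 4.3. Its numerator is the number of tablets taken; its denominator is "Number of tablets which should have been taken as directed by the investigator". Footnote 28 of the protocol flow chart sets the visits: "At Visits 6, 7, 8, 9 and EOT, compliance will be calculated for both Empagliflozin/placebo and BI 690517/placebo".

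Two other parts of the protocol bear on the weights. Under 6.2.5, EoT follows the premature stop of both drugs; if the last dose was on the day of a scheduled visit or the day before, "the scheduled visit should be performed as an EoT Visit". Under 3.3.4.1, a patient who stops only BI 690517/placebo may stay on the other drug and keeps attending scheduled visits. The same section provides for interruption and restart. SAP 7.3 has no rule for any of these situations, or for a missed visit.

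**The concern.** An average of percentages matches the overall percentage only when each interval is weighted by its own denominator. The listed weights do that for an uninterrupted course with visits on schedule. They stop doing so when the number of directed doses in an interval shrinks and the weight does not. That happens in three situations that the protocol foresees:

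1. **Early EoT.** The last interval may be a few days long but takes weight 4. Visit 7 performed as EoT would take weight 4 rather than 1.
2. **Stop of BI 690517/placebo alone.** Visits continue, so the visit interval stays at four weeks although few doses were due.
3. **Interruption.** Days on which the investigator directed no dosing leave the denominator, but the interval keeps weight 4.

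What is at stake is the accuracy of the per-patient compliance figure and its three categories, which readers use as background to the dose-response results.

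**Working it through.** **Reproducing the listed weights.** The flow chart puts Visits 5, 6, 7, 8, 9 and EoT at weeks 0, 1, 2, 6, 10 and 14. The successive differences are 1, 1, 4, 4 and 4, as listed. A patient who takes all 98 daily doses on schedule scores 100% by either method.

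**Formulas.** Let w be the listed weight, t the days taken and d the days directed in each interval. Three BI 690517/placebo tablets are due each day (Protocol 4.1.4), so ratios of days equal ratios of tablets.

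- SAP figure = Σ(w × 100 × t/d) / Σw, over the visits that have data. Dividing by the weights present is an assumption, because the SAP does not say.
- Pooled figure = 100 × Σt / Σd, which is the Protocol 4.3 ratio applied once to the whole period.

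**Illustrative patients.** The patterns are assumed. Intervals not mentioned are at 100%.

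| Pattern | SAP weights | Pooled |
|---|---|---|
| EoT 3 days after Visit 6, 2 of 3 taken | (100 + 4×66.7)/5 = 73.3% | 9/10 = 90.0% |
| EoT 3 days after Visit 7, 1 of 3 taken | (100 + 100 + 4×33.3)/6 = 55.6% | 15/17 = 88.2% |
| EoT 5 days after Visit 8, 2 of 5 taken | (100 + 100 + 400 + 4×40)/10 = 76.0% | 44/47 = 93.6% |
| 3 of 7 in each of weeks 1 and 2, then 3 of 3 before EoT | (42.9 + 42.9 + 400)/6 = 81.0% | 9/17 = 52.9% |
| EoT 2 days after Visit 7, one extra day's tablets taken | (100 + 100 + 4×150)/6 = 133.3% | 17/16 = 106.3% |
| BI 690517/placebo alone stopped 4 days after Visit 7, 2 of 4 taken, counted at Visit 8 | (100 + 100 + 4×50)/6 = 66.7% | 16/18 = 88.9% |
| Interruption leaves 4 directed days between Visits 7 and 8, 1 of 4 taken | (200 + 4×25 + 800)/14 = 78.6% | 71/74 = 95.9% |
| Same interruption, 2 of 4 taken | (200 + 4×50 + 800)/14 = 85.7% | 72/74 = 97.3% |

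Every row but the last changes category. Two rows show that errors are not all downward: one patient is raised from below 80% into the middle band, and one is raised from the middle band to above 120%.

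**How much weight the short interval carries.** If the earlier weights sum to W, a short final interval has share 4/(W+4). With all earlier intervals at 100%, the patient falls below 80% when compliance in the short interval is below (80(W+4) − 100W)/4 = 80 − 5W percent.

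| Last visit before the short interval | W | Share | Falls below 80% if short interval is under |
|---|---|---|---|
| Visit 6 | 1 | 80% | 75% |
| Visit 7 | 2 | 67% | 70% |
| Visit 8 | 6 | 40% | 50% |
| Visit 9 | 10 | 29% | 30% |

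One interrupted four-week interval in a full course also has W = 10, so by itself it changes the category only below 30%. With somewhat lower compliance elsewhere it takes less: 6/7, 6/7, 2/4, 25/28 and 26/28 give (85.7 + 85.7 + 200 + 357.1 + 371.4)/14 = 78.6%, against 65/74 = 87.8%.

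**Using the actual visit interval instead.** For the early EoT three days after Visit 7, the weight becomes 3/7 week: (100 + 100 + (3/7)×33.3)/(2 + 3/7) = 88.2%, equal to the pooled figure. For the stop of BI 690517/placebo alone and for the interruption, the visit interval is still four weeks, so 66.7% and 78.6% do not change.

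**The case against.** The best reply is that the SAP defines the weight as a time interval, and that the list only spells out the scheduled case. On that reading the early-EoT discrepancies disappear, as shown above. This part stands: for early EoT the problem is a conflict between a definition and its listed values. But the list assigns EoT a weight of 4 without qualification, so a programmer following it would use 4. The reading also leaves the other two situations unrepaired.

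A second reply is that the examples need both few directed doses and poor adherence within them, and that a patient who takes every directed tablet scores 100% either way. That is correct and limits how many patients are affected. Protocol 4.3 also prescribes no whole-period figure, and it uses the 80–120% band only to prompt a conversation with the patient. The pooled ratio is therefore a reasoned reference, not one the protocol imposes.

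A reader might go further and infer a false adherence gradient across doses, because Protocol 4.1.2 expects potassium to rise with dose and potassium drives interruptions and stops. The documents do not support that inference. They give no rates by arm, the errors run both ways, and potassium-driven stops concern BI 690517/placebo alone, so they do not by themselves lead to an early EoT. Nor is there support for inferring harm to the primary result: no visible text uses compliance for the FAS, the MMRM, MCPMod or the handling of intercurrent events.

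**Conclusion.** The point holds as a minor one. Applied as listed, the weights can misclassify some patients who stop early or interrupt, upward or downward. The discrepancy is large for the individual in the worked cases (for example 55.6% against 88.2%), but the number of patients affected cannot be estimated from the documents. Patients on schedule without interruption are not affected.

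The conclusion rests on three assumptions: weights are normalised to the visits with data; days on which no dose was directed drop out of the Protocol 4.3 denominator; and the patient patterns are illustrative. If interruption days stayed in the denominator, the interruption case would not arise in this form.

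The consequence is limited to a descriptive table. The rules for important protocol deviations are kept in a separate document that is not available here, so any use of the categories there could not be checked.

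**What to change.** In SAP 7.3, replace the weighted average with one ratio per patient: total BI 690517/placebo tablets taken, divided by total tablets directed over the whole BI 690517/placebo period, times 100. Assign the three categories from that ratio. Weighting each interval by its own number of directed tablets is equivalent.

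This covers all three situations and removes the conflict between the definition and the list. It costs one line of SAP text and a simpler derivation. The tablet counts are already collected, and the figure for on-schedule completers is practically unchanged.

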7.4 PRIMARY ENDPOINT(S)

7.4.1 Primary analysis of the primary endpoint(s)

The primary analysis of the primary endpoint will be analysed according to the primary strategy of handling ICEs (see [Section 5.1](#)).

Refer to Section 7.2.2 of the CTP for a description of the statistical analysis for the change from baseline in log transformed FMV UACR measured at 14 weeks of trial treatment.

The adjusted mean change in log transformed FMV UACR from baseline at 14 weeks and its standard error will be obtained from MMRM for the placebo and treatment groups. For the MMRM model, derived UACRs at baseline, visit 8, visit 9, and EoT, which were described in [Section 6.6.2.1](#), will be used.

SAS code for **the MMRM model** will be based on the following structure:

```
PROC MIXED DATA=alldat cl method=reml;

CLASS visit trt subject;

MODEL chg = baseline*visit visit*trt stratum / ddfm=kr s CL;

REPEATED visit / subject= subject type=un r rcorr;

LSMEANS visit*trt /pdiff=all om cl alpha=0.05 slice=visit;

RUN;
```

In the event of model non-convergence, the methods described in [Section 10.1](#) will be attempted (in order) to overcome it.

MCPMod Analysis

For the primary analysis the dose-response relationship will be modelled using following doses: placebo, 3mg, 10mg, and 20mg, in combination with empagliflozin or empagliflozin matching placebo, respectively. The multiple comparison procedure will then be implemented using optimal contrast tests which control the family-wise type I error rate at a one-sided $\alpha = 0.05$. For the MCPMod test, the optimal contrasts of each candidate model are calculated using the R-function optCont.

For the final evaluation, the contrast will be provided using the expected model means from the candidate set and the estimated variance-covariance matrix extracted from the MMRM model.

Once the significance of a dose-response signal is established, the dose-response profile and the target dose can be estimated using a model averaging approach for significant models.

To select a dose estimation model out of the set of significant models, estimates for each dose group will be calculated and will be based on the final dose-response model. The choice of the target dose will be based upon efficacy as well as considering safety and other relevant information.

[figure not shown]
The following displays are planned:

- Table of the updated contrast coefficients per dose group and candidate model, together with the MCPMod test statistics and p-values for each model and the critical value
- For averaging model, figure of the dose-response curve

- For all significant model shapes, figures of the dose-response curve plus 90% and 95% confidence bands (of the predicated shape) and 90% and 95% CIs per dose (estimated from MMRM)

- For all significant model shapes, figure with the placebo corrected dose-response curve plus 90% and 95% confidence band (of the predicated shape).

Estimates for each dose group will be calculated and will be based on the final dose-response model. R code to perform the evaluations is available in [Section 10.2](#).

